08 FEB 2019

Appendix B.

Table 8: TOXICITY TABLE

Laboratory Adverse Events							
Blood, Serum, or Plasma	Normal Range	Mild (Grade 1)	Moderate (Grade 2)	Severe (Grade 3)			
Creatinine – mg/dL (Female)	0.5 - 1.10	≥1.11 – 1.79	≥1.80-2.09	≥2.10			
Creatinine – mg/dL (Male)	0.6 - 1.35	≥1.36 – 1.79	≥1.80-2.09	≥2.10			
ALT U/L (Female)	6-29	30 - 105	106-175	>175			
ALT U/L (Male)	9-46	47 - 105	106-175	>175			
Hemoglobin (Female) - g/dL	11.7 – 15.5	11.0-11.6	9.5-10.9	<9.5			
Hemoglobin (Male) - g/dL	13.2 - 17.1	12.0 - 13.1	10.0 - 11.9	<10.0			
WBC Increase (Thousand/uL)	3.8 - 10.8	10.9 - 15.0	15.1 - 20.0	> 20.0			
WBC Decrease (Thousand/uL)	3.8 - 10.8	2.5-3.7	1.5-2.4	<1.5			
Absolute Neutrophil Count Decrease (cells/uL)	1500 - 7800	1490 - 1499	1000-1489	<1000			
Absolute Eosinophil Count Increase (cells/uL)	15 - 500	501-749	750-1500	>1500			
Platelets Decreased (Thousand/uL)	140 - 400	120-139	100-119	<100			

DMID/NIAID/NIH

108

CONFIDENTIAL

Phase I Study of HEV-239

Version 2.0

08 FEB 2019

Clinical Adverse Events								
Category	Mild (Grade 1)	Moderate (Grade 2)	Severe (Grade 3)					
Allergic reaction	Pruritus without rash*	Localized urticarial OR requires oral therapy	Generalized urticaria; angioedema OR anaphylaxis OR requires epinephrine					
Illness or clinical adverse event	Events that are usually transient and may require only minimal or no treatment or therapeutic intervention and generally do not interfere with the subject's usual activities of daily living.	Events that are usually alleviated with additional specific therapeutic intervention. The event interferes with usual activities of daily living, causing discomfort but poses no significant or permanent risk of harm to the research participant	Events interrupt usual activities of daily living, or significantly affects clinical status, or may require intensive therapeutic intervention. Severe events are usually incapacitating.					

* Not at injection site.

DMID/NIAID/NIH

109

CONFIDENTIAL

Phase I Study of HEV-239

Version 2.0

08 FEB 2019

Table 9: VITAL SIGNS REFERENCE RANGES

VITAL SIGNS	Mild (Grade 1)	Moderate (Grade 2)	Severe (Grade 3)
Fever (°C) *	38.0 - 38.4	38.5 - 38.9	≥39.0
Tachycardia - beats per minute	101 – 115	116 - 130	>130 or ventricular dysrhythmias
Bradycardia - beats per minute	45 - 50 bpm	40 – 44 bpm	<40 bpm
Hypertension (systolic)- mm Hg**	141-150	151-160	>160
Hypertension (diastolic) - mm Hg**	91-95	96-100	>100
Hypotension (systolic) - mm Hg**	85-89	80-84	< 80
Hypotension (diastolic) – mm Hg**	50 - 54	45 - 49	<45

* Oral temperature; no recent hot or cold beverages or smoking.

** Assuming subject is awake, and resting for AEs; 3 measurements on the same arm with concordant results.

DMID/NIAID/NIH

110

CONFIDENTIAL

Ig	Immunoglobulin
IM	Intramuscular
mITT	Modified intent-to-treat
MedDRA®	Medical Dictionary for Regulatory Activities
μg	Micrograms
MOP	Manual of Procedures
Ν	Number (typically refers to subjects)
NIH	National Institutes of Health

List of Abbr	List of Abbreviations (continued)	
ORF	Open reading frames	
PBMC	Peripheral Blood Mononuclear Cell	
PFS	Pre-filled syringe	
РР	Per protocol	
РТ	Preferred Term	
RCD	Reverse cumulative distribution	
SAE	Serious Adverse Events/Serious Adverse Experiences	
SDCC	Statistical and Data Coordinating Center	
SMC	Safety Monitoring Committee	
SOC	System Organ Class	
US	United States	
VLP	Virus Like Particle	
VTEU	Vaccine Treatment and Evaluation Unit	
WBC	White blood cell count	
WFI	Water for Injection	
WHO	World Health Organization	

1. **PREFACE**

The Statistical Analysis Plan (SAP) for "A Phase 1, Double-blinded, Placebo Controlled, Clinical Trial to Evaluate the Safety, Reactogenicity, and Immunogenicity of HEV-239 (Hecolin®) in a Healthy US Adult Population" (DMID Protocol 15-0108) describes and expands upon the statistical information presented in the protocol.

This document describes all planned analyses and provides reasons and justifications for these analyses. It also includes sample tables, listings, and figures planned for the final analyses. Regarding the final analyses and Clinical Study Report (CSR), this SAP follows the International Conference on Harmonisation of Technical Requirements for Registration of Pharmaceuticals for Human Use (ICH) Guidelines, as indicated in Topic E3 (Structure and Content of Clinical Study Reports), and more generally is consistent with Topic E8 (General Considerations for Clinical Trials) and Topic E9 (Statistical Principles for Clinical Trials). The structure and content of the SAP provides sufficient detail to meet the requirements identified by the Food and Drug Administration (FDA) and ICH, while all work planned and reported for this SAP will follow internationally accepted guidelines published by the American Statistical Association and the Royal Statistical Society for statistical practice.

This document contains four sections: (1) a review of the study design, (2) general statistical considerations, (3) comprehensive statistical analysis methods for immunogenicity and safety outcomes, and (4) a list of proposed tables and figures. Within the table, figure, and listing mock-ups (Appendices 1, 2, and 3), references to CSR sections are included. Any deviation from this SAP will be described and justified in protocol amendments and/or in the CSR, as appropriate. The reader of this SAP is encouraged to also review the study protocol for details on conduct of the study and the operational aspects of clinical assessments.

2. INTRODUCTION

Hepatitis E virus (HEV) is the most common cause of acute viral hepatitis worldwide causing an estimated 20 million infections, 3.3 million cases of symptomatic disease, and 70,000 deaths annually. [1, 2] The symptoms of acute HEV infection include fever, vomiting, myalgias, and malaise, followed by progression in some to jaundice, acholic stools, darkened urine, and elevated liver transaminases. [3] Adults are more likely to develop symptomatic disease than children, and pregnant women are most severely affected with mortality rates of 10 - 30% in the third trimester. Mother-to-infant transmission may also occur, resulting in fetal loss and increased perinatal morbidity and mortality. [4, 5] Unfortunately, supportive care is the only medical therapy available for hepatitis E. HEV is mainly transmitted via the fecal-oral route due to contaminated water although vertical and iatrogenic transmission from infected blood products can occur. HEV is responsible for sporadic cases and large outbreaks in the developing world and disproportionally affects areas with poor hygiene standards and population crowding such as refugee camps. [6, 7] Although less common, HEV also causes sporadic cases in industrialized nations, and the disease burden may be underestimated. [8]

HEV-239 is a 26kDa protein expressed in Escherichia coli as a non-fusion virus-like particle (VLP). It was licensed in 2012 for use in China and is produced and marketed by Xiamen Innovax Biotech Co. Ltd. HEV-239 encompasses the neutralizing epitope within the (P) domain (amino acid 368-606; 239 amino acids in length). The purified protein is adsorbed to aluminum hydroxide in buffered saline and then packaged into a pre-filled syringe for Intramuscular (IM) use. Approval and licensure in China was based on a Phase III clinical trial of HEV-239 conducted in 112,604 healthy Chinese adults (16-65 years). The study was a randomized, double-blinded, placebo-controlled (1:1 ratio) trial which evaluated the safety, immunogenicity, and efficacy of HEV-239 in subjects from 11 townships in the Jiangsu Province of China from August 2007 to June 2009. [9] Subjects were randomized to receive three doses of either 30 micrograms (µg) HEV-239 or placebo (a licensed hepatitis B vaccine) administered intramuscularly at 0, 1, and 6 months. The primary endpoint was prevention of hepatitis E during the 12 months following the 31st day after the third vaccine dose. Overall, the vaccine was well tolerated with similar systemic adverse events (AEs) but slightly higher rates of swelling and pain in HEV-239 recipients in comparison to placebo. Serious adverse events (SAEs) and deaths were similar between the groups. SAEs within 30 days of any dose (0.4% versus 0.4%), SAEs after the 30 day window periods (2.5% versus 2.5%), and deaths (0.2% versus 0.2%, none were considered related) were similar between vaccine and placebo recipients respectively. SAEs that were reported in the Phase 3 study were considered unrelated to study vaccine by the Data Safety Monitoring Board (DSMB). In subjects who received either 2 or 3 doses of vaccine, 100% protection against pre-specified hepatitis E infection was observed. [9] A follow-up study was subsequently conducted through 4.5 years for evidence of hepatitis E infection. [10] In that study, 7 cases of hepatitis E were identified in vaccine recipients versus 53 in placebo recipients. [10]

A vaccine against HEV that has undergone safety and immunogenicity testing outside of China would be very beneficial. Such a vaccine could provide protection for travelers or be used in outbreaks to prevent continued transmission of disease. It also would be highly beneficial in preventing maternal, fetal, and infant deaths. The vaccine, though licensed in China, is neither FDA approved nor World Health Organization (WHO) prequalified. Although vaccine safety is established in a Chinese population, safety in other population cannot be presumed. Data are needed establishing its safety and immunogenicity in other populations. This Phase I study will use the dose ($30 \mu g$), dosing schedule (0, 1, and 6 months), and route of administration (IM) that was used in the Phase 3 study in China.

The purpose of this Phase 1 randomized-controlled double-blind study is to assess the safety, reactogenicity, and immunogenicity of HEV-239 in healthy adults in the U.S. Twenty-five subjects will be randomized (4 vaccine: 1 placebo) to receive vaccine (n = 20) or placebo (n = 5). Each subject will receive 3 injections,

either vaccine or placebo at Days 1, 29, and 180. Subjects will be followed through 12 months for safety and durability of the immune responses observed.

2.1. Purpose of the Analyses

These analyses will assess the safety, reactogenicity, and immunogenicity of HEV-239 administered in three successive intramuscular injections and will be included in the clinical study report.

3. STUDY OBJECTIVES AND ENDPOINTS

3.1. Study Objectives

3.1.1. Primary

- Assess the safety and reactogenicity of HEV-239 following delivery of each vaccine dose.
- Assess the number of subjects with ≥4-fold rise in HEV Immunoglobulin (Ig) G at any time after vaccination.

3.1.2. Secondary

- Assess the number of subjects with HEV IgM seroconversion at any time after vaccination.
- Assess the number of subjects with HEV IgG seroconversion at any time after vaccination.
- Assess the HEV IgG geometric mean concentrations (GMCs) at any time after vaccination.

3.2. Endpoints

3.2.1. Primary

- Determine the number of solicited local and systemic reactogenicity events from the time of study vaccination through Day 8 after each study vaccination.
- Determine the number of vaccine-related unsolicited adverse events (AE) from the time of each study vaccination through Day 29 after each study vaccination.
- Determine the number of clinical safety laboratory AEs at Day 8 after each study vaccination.
- Determine the number of vaccine-related serious adverse event (SAE) from the time of first study vaccination through 6 months after the last dose of vaccine.
- Determine the number of subjects showing ≥4-fold rise in serum HEV IgG concentration by Enzymelinked Immunosorbent Assay (ELISA) from the baseline at Days 8, 15, 29, 36, 43, 57, 180, 187, 194, 208, and 360.

3.2.2. Secondary

- Determine the number of subjects with HEV IgM seroconversion by ELISA at Days 8, 15, 29, 36, 43, 57, 180, 187, 194, 208, and 360.
- Determine the number of subjects with HEV IgG seroconversion by ELISA at Days 8, 15, 29, 36, 43, 57, 180, 187, 194, 208, and 360.
- Determine the HEV IgG GMCs by ELISA in subjects at Days 1, 8, 15, 29, 36, 43, 57, 180, 187, 194, 208, and 360.

3.3. Study Definitions and Derived Variables

The baseline value will be defined as the last value obtained prior to the first vaccination/dose of study product.

Seronegative samples will be defined as per the Wantai HEV-IgM and IgG ELISA package inserts (Absorbance Value / Cut-Off Value (A/C.O.) <0.9).

Seroconversion will be defined as a change from a seronegative result to a seropositive result as defined by the Wantai HEV-IgM and IgG ELISA package inserts (A/C.O. >1.1). Samples with borderline A/C.O. values (0.9-1.1) will be retested in duplicate. If both retests are negative (as defined above), the result will be reported as negative. If one or both retests are positive, the result will be reported as positive. If both retest values are in the borderline zone, the result will be reported as indeterminant.

A 4-fold seroconversion will be defined as a HEV IgG ≥ 0.154 in a subject that was HEV seronegative at baseline.

Duration of solicited events will be defined as the number of contiguous symptomatic days.

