2.3 Potential Risks and Benefits

2.3.1 Potential Risks

The potential risks of participating in this trial are those associated with having blood drawn, the IM injection and possible reactions to the HEV-239 vaccine with aluminum adjuvant, and breach of confidentiality.

Drawing blood may cause transient discomfort and fainting. Fainting is usually transient and managed by having the subject lie down and elevate his/her legs. Bruising at the blood draw site may occur but can be prevented or lessened by applying pressure to the blood draw site for a few minutes after the blood is taken. IM injection may also cause transient discomfort and fainting. Drawing blood and IM injection may cause infection. The use of aseptic (sterile) technique will make infection at the site where blood will be drawn or where the study vaccination will be given extremely unlikely.

There is a small amount of risk to subjects who report that they are in good health but who may have an unknown health problem at the time of screening. This trial will screen by physical exam, history, and vital signs. The following baseline laboratories will be obtained at screening on all subjects to determined eligibility.

Baseline Laboratories:

- Hematology
 - Complete blood count with differential (which will include white blood cells, the absolute neutrophil count (ANC), the absolute eosinophil count (AEC), hemoglobin, and platelets).
 - A WBC evaluation may include any abnormal cells, which will then be reported by the laboratory. A hematology evaluation may include abnormalities in the red blood cell (RBC) count and/or RBC parameters

DMID/NIAID/NIH

CONFIDENTIAL

and/or RBC morphology, which will then be reported by the laboratory. In addition, any other abnormal cells in a blood smear will also be reported.

- Chemistry (fasting or non-fasting)
 - o Creatinine
 - o Glucose
 - Alanine aminotransferase (ALT)
- Serology
 - Hepatitis B surface antigen
 - Hepatitis C antibody
 - HIV types 1 and 2 antigen/antibody
 - Hepatitis E virus IgM and IgG antibodies
- Serum pregnancy test (in women of childbearing potential)
- Urine
 - A urine drug screen will be obtained

Safety laboratories will be obtained on Day 8 after each vaccine dose and also before the Day 180 vaccination. To minimize risks, subjects will not receive the subsequent study vaccinations if a related Grade 3 laboratory abnormality occurs. The following safety laboratories will be obtained on all subjects to determined safety.

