5.1 Eligibility Criteria

Screening for eligible subjects must be performed within 28 days before Day 1. The investigator should ensure that all study enrollment criteria have been met at the end of the screening period. If a subject's status changes (including laboratory results or the receipt of additional medical records) after screening but before the prime vaccination such that the subject no longer meets all eligibility criteria, then the subject should be excluded from participation in the study.

Enrollment will be based solely on the eligibility criteria outlined below and will be open to both sexes and all races/ethnicities. Sex and minority breakdown cannot be predicted for this study but should follow the general population distribution. Pregnant women and women who are breastfeeding will not be eligible for inclusion.

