5.1.2 Subject Exclusion Criteria

Prospective subjects must not meet any of the following exclusion criteria to be considered eligible for enrollment:

- 1. Has a previous HEV infection or chronic liver disease.
- 2. Has received any experimental agent¹⁰ within 30 days prior to first vaccination, or the expected recipient of any experimental agent during this trial-reporting period. ¹⁰Including vaccines, drugs, biologics, devices, and/or blood products
- 3. Female subject is pregnant (or has a positive pregnancy test prior to vaccination) or breast feeding, or planning to become pregnant within 3 months after the last boost vaccination.

DMID/NIAID/NIH

- 4. Fever (≥38.0°C/100.4°F) or other acute illness within 3 days prior to first vaccination.
- 5. Infection requiring systemic antibiotics or antiviral treatment within the 7 days prior to first vaccination.
- 6. Has a positive urine drug screen for amphetamines¹¹, cocaine, opiates, or phencyclidine.

¹¹Prescription amphetamines are not exclusionary.

7. Chronic, clinically significant medical or psychiatric conditions that,¹² in the opinion of the investigator, may pose additional risk to the subject if she/he participates in the study.

¹²Permissible conditions include but are not limited to mild, wellcontrolled asthma, well-controlled depression, well-controlled anxiety, seasonal allergies, and well-controlled hypertension.

8. Receipt of immunosuppressive drugs¹³⁻¹⁵ or biologic agents within the 30 days prior to enrollment.

¹³This includes use of oral or parental prednisone. This also includes allergy desensitization injections from 14 days prior to each vaccination through 14 days after each vaccination. The use of topical steroids for mild uncomplicated dermatitis permissible after therapy is completed. Over-the-counter (OTC) corticosteroid nasal sprays for allergic rhinitis are permissible. The use of low or moderate dose inhaled steroids is permissible. Doses are defined as per age as using inhaled high-dose per reference chart in the National Heart, Lung and Blood Institute Guidelines for the Diagnosis and Management of Asthma (EPR-3) or other lists published in UPTODATE.

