6.3.1.10 Visit 11, Day 180 +/- 14 Days from Prime Vaccination; Clinic Visit

Prior to Vaccination

- Review medical history for any interval changes
- Review concomitant medications
- Obtain vital signs (HR, BP, and oral temperature)
- Subjects who have a diastolic blood pressure value >90 mmHg or a systolic blood pressure value >140 mmHg prior to the prime vaccination can receive the vaccination if the elevated blood pressure is considered to be not clinically significant and the subject had acceptable blood pressure at screening.
- Perform symptom-directed PE (if needed).
- Perform urine pregnancy test for women of childbearing potential within 24 hours prior to immunization. Test result must be known and negative prior to vaccination.
- Review of birth control history with female subjects.

DMID/NIAID/NIH

- Counsel subjects to use adequate birth control methods to avoid pregnancy.
- Obtain blood for safety laboratories (Section 2.3.1).
- Obtain serum for immunogenicity assays.
- Collect PBMCs and plasma for future assays
- Review inclusion and exclusion criteria to ensure the subject remains eligible for boost vaccination
- Study vaccine will be prepared on-site by an unblinded site research pharmacist (see Section 4.3).
- Pre-administration reactogenicity assessments will be performed prior to vaccination to establish baseline. A subject with mild pre-administration reactogenicity which is transient, resolving, or clinically insignificant may receive vaccination at the investigator's discretion.

Vaccination

- The unblinded study vaccine administrator will vaccinate the subject according to vaccination assignment in the subject's preferred arm.
- Following receipt of study product, subjects may have the injection site covered with an adhesive bandage (e.g. BAND-AID®) as needed.

Following Vaccination

- Observe subjects for a minimum of 30 minutes following immunization.

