9.6. Clinical Laboratory Evaluations

Clinical safety laboratory parameters will be collected at Baseline (screening visit) and Study Days 8, 36, 180, and 187. If indicated by symptoms they may also be evaluated at Study Day 15, 43, 194 or at Early Termination/Unscheduled visits.

Chemistry parameters to be evaluated include creatinine and alanine aminotransferase (ALT). Hematology parameters to be evaluated include white blood cell count (WBC), absolute neutrophil count (ANC), the absolute eosinophil count (AEC), hemoglobin, and platelets. Grading scales for safety laboratory parameters are presented in Table 6.

The distribution of laboratory results by severity, time point, and treatment group will be presented in Table 48, Table 49, Table 50, Table 51, Table 52, and Table 53 for chemistry and beginning at Table 56 and concluding at Table 67 for hematology. Descriptive statistics including mean, standard deviation, median, minimum and maximum values by time point, for each laboratory parameter, will be summarized in Table 54, Table 55, Table 68, Table 69, Table 70, Table 71, and Table 72. Changes in laboratory values will be presented in Figure 21, Figure 22, Figure 23, Figure 24, Figure 25, Figure 26, and Figure 27.

Subject visits with abnormal laboratory results, Grade 1 severity or higher, will be presented in Table 46 and Table 47.

Listing 11 and Listing 12 will provide a complete listing of individual clinical laboratory results with applicable reference ranges.

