			M Gra	ild/ de 1	Mod Gra	erate/ de 2	Sev Gra	ere/ de 3
Time Point	Treatment Group	Ν	n	%	n	%	n	%
Day 8	HEV-239	х	х	xx	х	XX	х	XX
	Placebo							
Day 36	HEV-239							
	Placebo							
Day 187	HEV-239							
	Placebo							
Max Severity Post Baseline	HEV-239							
	Placebo							

Note: The "Max Post Baseline" rows indicate the maximum severity experienced by each subject at any time point post baseline, including unscheduled assessments. N=Number of subjects in the Safety Population

Tables with similar format:

 Table 53:
 Abnormal Laboratory Results Related to Study Treatment by Parameter, Maximum Severity, Time Point, and Treatment Group

 - ALT

Time Point	Treatment Group	Ν	Mean	Standard Deviation	Median	Min, Max
Baseline	HEV-239	х	xx.x	XX.X	XX.X	XX.X, XX.X
	Placebo					
Day 8	HEV-239					
	Placebo					
Day 8, Change from Baseline	HEV-239					
	Placebo					
Day 36	HEV-239					
	Placebo					
Day 36, Change from Baseline	HEV-239					
	Placebo					
Day 187	HEV-239					
	Placebo					
Day 187, Change from Baseline	HEV-239					
	Placebo					

Table 54: Laboratory Summary Statistics by Parameter, Time Point, and Treatment Group – Creatinine

Note: N=Number of subjects in the Safety Population

Tables with similar format:

Table 55: Laboratory Summary Statistics by Parameter, Time Point, and Treatment Group – ALT

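### The laboratory summary tables leave out the pre-Dose-3 (Day 180) sample, so a grade already present before Dose 3 is counted at Day 187 and cannot be told from a new one

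*SAP*

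**What the plan says.** - **Baseline.** SAP 3.3: "The baseline value will be defined as the last value obtained prior to the first vaccination/dose of study product". SAP 9.6 names the laboratory baseline and the sampling days: "Clinical safety laboratory parameters will be collected at Baseline (screening visit) and Study Days 8, 36, 180, and 187". The schedule of events has no hematology or chemistry draw on Day 1 or Day 29.
- **Pre-Dose-3 sample.** Protocol 2.3.1: "Safety laboratories will be obtained on Day 8 after each vaccine dose and also before the Day 180 vaccination". Protocol 6.3.1.10 (Visit 11) places this draw among the steps before vaccination.
- **Primary laboratory endpoint.** SAP 3.2.1: "Determine the number of clinical safety laboratory AEs at Day 8 after each study vaccination". The neighboring endpoints for unsolicited AEs and SAEs are limited to vaccine-related events. This one is not. Grades come from the fixed limits in SAP Table 6.
- **Tables.** Summary Tables 54-55 and 68-72 show baseline, Days 8, 36 and 187, and changes such as "Day 187, Change from Baseline". Severity Tables 48-50 and 56-61, and the related-results Tables 51-53 and 62-67, use the same post-baseline days. None has a Day 180 row.
- **Other displays.** Figures 21-27 plot mean change from baseline at Days 8, 36, 180 and 187. Tables 46-47 list subject visits with Grade 1 or higher results, and Listings 11-12 give every result.

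**The concern.** The primary laboratory endpoint is framed dose by dose, but its tables offer only a reference taken before the whole series. For Dose 1 that reference is recent. For Dose 3 it is about half a year old and precedes two vaccinations. Two consequences follow.

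First, change from baseline means something different at each dose, and at Day 187 it does not isolate what happened after Dose 3.

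Second, the Day 187 severity row shows the grade on that day with nothing beside it for the grade a week earlier. A raised ALT present on Day 180 and still present on Day 187 looks the same in the summary as one that first appeared after Dose 3.

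The rest of the plan does little to fill the gap. Protocol 5.2 does not list the normal-laboratory inclusion criterion (criterion 5) among those rechecked before Doses 2 and 3. Non-serious unsolicited AEs are not collected between Day 57 and Day 180 (Protocol 8.2). Concomitant therapies between Day 57 and Day 150 are recorded only in conjunction with SAEs (Protocol Appendix A). The Day 180 sample is therefore the main record of a subject's laboratory status just before Dose 3.

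**Working it through.** **Inputs.** Screening window, Protocol 5.1: "Screening for eligible subjects must be performed within 28 days before Day 1", that is 1 to 28 days before Day 1. Dose 3 window, Protocol 6.3.1.10: Day 180 ± 14. Post-Dose-3 draw, Protocol 6.3.1.12: Day 8 after Dose 3, ± 1 day, so 6 to 8 days after the dose. Vaccinees: 20.

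**Age of the reference sample.** Elapsed days = (study day − 1) + days from screening to Day 1.

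- Day 8, after Dose 1: 7 + 1 = 8 to 7 + 28 = 35 days.
- Day 36, after Dose 2: 35 + 1 = 36 to 35 + 28 = 63 days.
- Day 187, after Dose 3: 186 + 1 = 187 to 186 + 28 = 214 days.
- Day 187 with all windows: earliest is Dose 3 on Day 166 and the draw 6 days later (Day 172), 171 + 1 = 172 days. Latest is Dose 3 on Day 194 and the draw 8 days later (Day 202), 201 + 28 = 229 days.
- From the pre-Dose-3 sample to the same draw: 7 days (6 to 8).

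**Does a pre-existing abnormality enter the Day 187 count?** Two protocol rules bear on this.

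- Protocol 8.5 treats any result that meets the grading scale as an adverse event. Under that rule it counts.
- Protocol 7.2.1.2 asks for values whose toxicity grade has increased after vaccination, but does not name the sample to compare with. Under the SAP's single baseline the comparator is screening. Screening values must be within site normal limits, apart from minor abnormalities that are not clinically significant, so nearly any later grade is an increase and again counts. Only if the comparator were the pre-Dose-3 sample would it drop out, and no text says so.

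**Size.** One affected vaccinee is 1/20 = 5 percentage points of the Day 187 rate. The plan's only sample-size figure is the chance of seeing at least one event among 20, 1 − (1 − p)^20. At p = 10% this gives 1 − 0.9^20 = 87.84%, which reproduces SAP Table 2. If 10% of vaccinees carried an abnormality from before Dose 3 through to Day 187, the chance that at least one did would therefore be 88%. At 5% it is 1 − 0.95^20 = 64%. Both carriage rates are assumptions; the documents give none.

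**Internal check on the tables.** The maximum-severity row in Tables 48-50 and 56-61 takes any post-baseline time point, including unscheduled ones. A Day 180 grade can therefore enter that row without appearing in any time-point row above it.

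**The case against.** The strongest reply has four parts.

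1. *The endpoint is a count of graded events, not a change score.* This stands. Change from baseline is a descriptive row, the trial tests no hypothesis, and grades do not depend on any baseline. A reader might infer that the trial measures the Dose 3 laboratory effect as change from screening, or that drift will be read as a Dose 3 effect. No passage says either.
2. *Day 180 data are already reported.* This stands in part. Figures 21-27 show group means at Day 180 next to Day 187. Tables 46-47 and Listings 11-12 let a reader trace each of 25 subjects by hand. But mean curves cannot show whether an individual's grade predated Dose 3, and a listing does not produce a count.
3. *Attribution handles it.* Blinded investigators record attribution for abnormal results, related results have their own tables, and placebo is shown beside vaccine. So the pre-dose sample is not the only means of separating a Dose 3 effect from drift. Still, the endpoint count includes unrelated results, and SAP 4.2 says the five placebo subjects are not meant as a comparison group.
4. *A single vaccine-naive baseline is right for a three-dose series.* This stands, and it limits the remedy. Day 180 follows Doses 1 and 2, so replacing screening by Day 180 in the count would remove abnormalities persisting from those doses. With no draw on Day 1 or Day 29, only Dose 3 can have an immediate pre-dose reference.

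A seasonal explanation is also tempting. Protocol 5.1.2 permits "seasonal allergies, and well-controlled hypertension", and the eosinophil count is graded for increases. The documents give no size for any seasonal shift, so the point does not rest on it.

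**Conclusion.** The concern holds as a gap in the summary tables. The baseline is a defensible choice, but at Day 187 it is about 187 to 214 days old, against 8 to 35 days for Dose 1, and the tabulated change cannot be assigned to Dose 3 alone. The sample that would help is drawn 7 ± 1 days earlier and is missing from Tables 48-72. Any abnormality carried into Dose 3 counts at Day 187 at 5 percentage points per vaccinee, with no summary table to separate it.

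The intervals rest only on the schedule and its windows. The number of subjects who would be affected is unknown. The documents do not support saying that the planned results would be biased in a known direction or by a known amount, and no sample-size figure changes.

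**What to change.** Keep screening as the overall baseline, and keep the existing Day 187 counts and change rows. Add the following:

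- A Day 180 (pre-Dose 3) row in severity Tables 48-50 and 56-61 and in summary Tables 54-55 and 68-72.
- A row for the change from Day 180 to Day 187 in Tables 54-55 and 68-72.
- Beside the primary laboratory endpoint count, by arm, the number of Day 187 laboratory grades that are new or higher than the pre-Dose-3 grade. Label it as supplementary and as available for Dose 3 only.
- A sentence in SAP 3.3 and 9.6 naming the reference sample used by each row.

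The sample is already scheduled and Figures 21-27 already use it, so no visit, blood draw or assay is added. The cost is SAP wording, one derived variable and a few table rows. Because the additions sit beside the screening-based results, abnormalities persisting from Doses 1 and 2 remain in the count.
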